10.10 Analysis of Safety

All safety summaries will be presented using the safety dataset and comparing across all treatment groups unless otherwise noted.

The extent of exposure to study treatment will be quantified using the parameters total dose (mg), number of doses, and duration of exposure (days). Total dose and duration of dosing will be summarized using descriptive statistics while number of doses will be presented by counts and percentages. All drug exposure data will be listed and summarized by treatment group.

Percent compliance and the number of missed doses will be summarized using descriptive statistics for overall study and by treatment group. Compliance will also be presented according

to range categories and summarized by counts and percentages.

For AEs, the investigator's verbatim term of each AE will be mapped to system organ class and preferred term using the current version of MedDRA. Adverse events will be summarized by system organ class and preferred term; a participant will only be counted once per system organ class and once per preferred term within a treatment group. Participant counts and percentages and event counts will be presented for each treatment group by decreasing frequency for the following summaries; all treatment emergent adverse events (TEAEs), all SAEs, all TEAEs by maximum severity, all TEAEs by relationship to study treatment, all TEAEs related to study treatment.

Listings will also be presented by subject for all AEs as well as for SAEs, AEs leading to discontinuation from the study and AEs leading to discontinuation from study treatment. These listings will include treatment group and study period along with variables describing the nature, duration, and resolution of the event.

All AEs listed above will be presented separately by study period (on-treatment period or follow-up period) as well as overall for the study. Study period will be based on planned timing of visits (as outlined in Section 7) as opposed to whether particular participants were using study product or not. Adverse events will be split in to two groups: signs and symptoms of genital irritation considered to be possibly, probably and definitely related to study product (as defined in section 10.2.3 judged not to be due to pathogen or iatrogenic trauma); and all other AEs (non-genital). A summary of genital AEs will also be presented split out by AE grade as determined by the DAIDS toxicity grades. All AE summaries will be presented for both the safety and the Per-Protocol datasets.

All AEs determined to be signs or symptoms of genital irritation with a perceived potential causality to study product (*i.e.* assessed as Definitely, Probably, or Possibly Related) will be compared between treatment groups and exact 95% confidence limits will be displayed. The 95% confidence interval will be determined from the Poisson (incidence rate) distribution. The incidence of genital AEs will be compared across treatment groups using Cochran–Mantel-Haenszel (CMH) test controlling for study center.

A similar comparison will also be performed for incidence of reported signs of genital irritation irrespective of assigned causality.

All AEs will be reviewed by the Investigator and Sponsors at the end of the study in a blinded review to ensure that signs of genital irritation are correctly identified as part of the data-cleaning process.

The incidence of candidiasis and use of rescue therapy for BV relapse will be presented across all treatment groups.

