3.2 Secondary Objectives and Endpoints

The secondary objectives of the study are as follows:

- To explore the microbiological and overall efficacy of 3% SPL7013 Gel in the treatment of BV compared to the HEC placebo gel.
- To determine the safety and tolerability of SPL7013 Gel in the study population.
- To determine the Investigator-assessed and patient perceived symptom resolution and treatment acceptability of SPL7013 Gel in the study population.
- To assess the association of BV signs and symptoms with clinical diagnosis of BV.

These will be determined by comparison of the following Secondary Endpoints:

- "Nugent Cure" (defined as a Nugent score of ≤3 when a score of 7 or more was determined at Baseline) at Visit 3 and the TOC visit.
- "Therapeutic Cure" (defined as a composite of both "Clinical Cure" and a Nugent score of 3 or less irrespective of status at Baseline) at Visit 3 and the TOC visit.
- "Therapeutic Resolution of BV" (defined as a Nugent score of ≤6 and fulfilling the criteria of "Clinical Cure") at Visit 3 and the TOC visit.
- "Clinical Cure" at Visit 3.
- Genital AEs considered to be possibly, probably or definitely related to study product.
- All other AEs.
- Change from baseline in "Symptom Questionnaire" score at Visit 3 and TOC visit.
- "Acceptability Questionnaire" (Treatment Satisfaction Questionnaire for Medication (TSQM)) domain scores at Visit 3
- Correlation of Symptom Questionnaire responses with Nugent score at Visit 3 and TOC.
- Semi-quantitative analysis of vaginal flora (sub-set only)

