6.11 Warnings

Based on the animal pharmacokinetic and toxicology data and the clinical data from the human studies, the following events may be experienced by women following application of SPL7013 Gel or HEC placebo gel:

- Metrorrhagia;
- Genitourinary erythema;
- Vaginal discharge of a curdled white material;
- Genitourinary discomfort/pain;
- Genitourinary pruritus;
- Dyspareunia;
- Burning sensation;
- Dysuria;
- Bacterial vaginosis;
- Headache;
- Respiratory Tract Infection;
- Lymphadenopathy.

This list represents the most commonly reported AEs observed during the clinical studies to date, irrespective of perceived causality to study product. Although not expected, other risks that are currently unknown may be associated with the treatment.

Systemic absorption of SPL7013 following vaginal administration of SPL7013 containing gels has not been observed in either animal or human studies.

The reproductive effects of SPL7013 Gel have not been investigated in clinical trials. The effects of SPL7013 Gel on the developing human fetus and breast-feeding child are also unknown. For these reasons, participants of childbearing potential must agree to use adequate contraception (*i.e.* hormonal contraceptive (but not vaginal rings), IUD, sterilization or vasectomy) prior to study entry and for the duration of the study. The chosen method of contraception must be fully effective upon entry in to the study. Women recruited in to this study will undertake a pregnancy test prior to the first dose of study medication and at the Baseline and final Follow-Up visits. Should a woman become pregnant or suspect that she is pregnant while participating in the study, she should inform study staff and her primary care physician immediately. Site staff will immediately report any pregnancy to the Investigator and procedures should be followed as outlined in Section 8.9. Participants found to be pregnant will not use any further study product but every attempt will be made by study staff to follow the pregnancy for the outcome. In addition, women who are breast-feeding are not to be enrolled in to the study.

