10.2.2 Secondary Endpoints

The endpoints for evaluation of secondary study objectives (Secondary Endpoints) are as follows:

- "Nugent Cure", "Therapeutic Resolution of BV" and "Therapeutic Cure" at the TOC visit
- "Clinical Cure", "Nugent Cure", "Therapeutic Resolution of BV" and "Therapeutic Cure" at Day 9-12 (Visit 3)
- Both Investigator-assessed and patient perceived resolution of symptoms compared to Baseline, as determined in the "Symptom Questionnaire"
- Genital AEs considered to be possibly, probably, definitely related to study product
- All other AEs
- Acceptability of study treatment as determined in the "Acceptability Questionnaire" (the TSOM).
- To assess the correlation of BV signs and symptoms (via Symptom Questionnaire) with clinical diagnosis of BV
- Semi-quantitative analysis of vaginal flora (sub-set only)

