10.2.3 Definition of Signs and Symptoms of Genital Irritation

The following cluster of symptoms will be employed in determining the number of women with signs and symptoms of genital irritation, and will be actively solicited in the CRF and diary card:

Symptoms:

Pelvic pain; vaginal and vulvar pain; tenderness; vulval itching, edema, erythema, lesions (vesicles, blisters, erosions, ulcers), or rash; vaginal itching, dryness, excessive discharge; dysuria; vulvovaginitis; or dyspareunia.

Signs:

Vulval edema, erythema, lesions (vesicles, blisters, erosions, ulcers), or rash; vaginal edema, erythema, excessive discharge or lesions; cervical edema, erythema, discharge, or lesions; vulvovaginitis; or cervicitis.

Each AE considered to be a symptom or sign of genital irritation will be identified as such in the CRF, and additionally will be noted as either being reported by participant (either spontaneously or in the diary card) or detected at pelvic/genital exam.

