16.3 Follow-up Evaluations

16.3.1 Clinical Evaluation upon Reporting GU Symptoms

| Condition / Complaint | Study Gel Use | Evaluation | Follow up and Treatment Action |
|--|--|--|--|
| Vulval irritation, swelling, sores | Hold study gel use until evaluated (within 24 hours) | Genital examination | Follow up according to signs provided in Table 2 below. If antibiotic treatment required patient must cease treatment, but is to continue study visits. If no significant clinical signs, restart treatment with agreement of patient at the discretion of the investigator. |
| Dysuria, frequency of micturition | Hold study gel use until evaluated (within 24 hours) | Urine dipstick and midstream urine for culture and antimicrobial sensitivity testing | If antibiotic treatment required, patient must cease treatment, but is to contine study visits. Reinstate study gel with agreement of patient at the discretion of the investigator if symptoms resolve within 24-48 hours, otherwise withdraw patient. |
| Vaginal discomfort, superficial Dyspareunia, vaginal discharge (change from normal) | Hold study gel use until evaluated (within 24 hours) | Genital and vaginal speculum examination. Bimanual pelvic exam if pelvic pain | Follow-up according to signs provided in Table 2 below. If no significant signs are observed, re-instate study gel with the permission of the patient at discretion of the investigator |
| Intermenstrual Bleeding /Spotting | Hold study gel use until evaluated (within 24 hours) | Genital and vaginal speculum examination | If determined to be endometrial bleeding with no other source, re-instate study gel use with the agreement of the patient at the discretion of the investigator. Reevaluate in 24-48 hours if the participant reports the bleeding / spotting has not resolved. |
| SAE that is judged by the site investigator or designee to be definitely, probably, possibly, | For Grades 1,2, and 3 – Hold study gel use until evaluated (within 24 hours) | Evaluate as according to current clinical practice at the site | Provide treatment as clinically indicated. If resolved within 24-48 hours, reinstate study gel use with patient's permission at investigator's discretion. If antibiotic treatment required, patient cease treatment, but is to continue study visits. |
| or probably not related to the study gel | For Grade 4 – Permanent Discontinuation | Not Applicable | Not Applicable |

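### Section 10.10 labels every AE outside the related genital-irritation list non-genital, so related intermenstrual bleeding is misclassified against the undefined 'genital AE' endpoint

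*Protocol*

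**What the plan says.** **Endpoint.** Section 3.2 lists "Genital AEs considered to be possibly, probably or definitely related to study product" and Section 10.2.2 lists "Genital AEs considered to be possibly, probably, definitely related to study product". The synopsis agrees. In each place all other AEs follow as a separate endpoint. None of them defines a genital AE.

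**Irritation list.** Section 10.2.3 defines signs and symptoms of genital irritation by enumeration. The symptoms run from pelvic, vaginal and vulvar pain to "vaginal itching, dryness, excessive discharge; dysuria; vulvovaginitis; or dyspareunia"; the signs end with "cervical edema, erythema, discharge, or lesions; vulvovaginitis; or cervicitis". No wording leaves the list open to further terms.

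**Analysis.** Section 10.10 divides AEs into two groups. The first holds signs and symptoms of irritation under 10.2.3 that are judged related to product and not caused by a pathogen or iatrogenic trauma. The second is "and all other AEs (non-genital"). The comparison between arms, with exact limits, is of "All AEs determined to be signs or symptoms of genital irritation with a perceived potential causality to study product"; the next sentences give the confidence-interval method and a Cochran-Mantel-Haenszel (CMH) test of genital AE incidence controlling for center. A further comparison covers irritation signs whatever the causality.

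**Events expected.** Section 6.11 includes metrorrhagia in its warnings and adds: "This list represents the most commonly reported AEs observed during the clinical studies to date, irrespective of perceived causality to study product". Section 16.3.1, the table for reported genitourinary symptoms, has a row for "Intermenstrual Bleeding /Spotting".

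**The concern.** The endpoint is worded by body site and relatedness. The analysis groups are built from a list of irritation terms, and whatever is left is then given a site label that does not fit it. A genital event that is judged related but is not an irritation term meets the endpoint as worded, yet is filed as non-genital.

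The trial is meant to show which gel strengths suit further development (Section 2.7), so local tolerability by strength is a result readers will look for. If related bleeding differed between strengths, the row headed as genital and its test would not reflect it, and a reader taking the non-genital heading at face value would not look for bleeding there.

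**Working it through.** No arithmetic applies. The protocol gives no rates of related bleeding or of irritation, so the check is a comparison of texts.

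**Step 1: terms against the 10.2.3 list.** Metrorrhagia, bleeding and spotting are absent from both symptoms and signs. Pain, itching, dysuria, dyspareunia, erythema and discharge are present. The words burning and discomfort are absent too, but see the objection below.

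**Step 2: does the protocol regard bleeding as genital?** Section 16.3.1 places it among genitourinary symptoms and evaluates it by genital and speculum examination. Section 6.11 lists metrorrhagia among the frequent events of earlier studies. Nothing in the protocol suggests that it lies outside the genital tract.

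**Step 3: follow each kind of event through Section 10.10.**

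| Event | Group in the two-way split | Formal comparison of related events | Any-causality comparison of irritation signs | Preferred-term tables by arm |
|---|---|---|---|---|
| Listed irritation sign, related, no pathogen or trauma | Irritation | Yes | Yes | Yes |
| Metrorrhagia, related | Non-genital | No, on the contextual reading | No | Yes, including related events |
| Listed irritation sign, judged unrelated | Non-genital | No | Yes | Yes, under all events |
| Listed irritation sign, due to a pathogen | Non-genital | Only if also judged related; the exclusion is not repeated there | Yes | Yes |

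The second row is the main fault. The event satisfies the endpoint as worded in 3.2 and 10.2.2, and its causality is accepted, so neither the relatedness condition nor the pathogen and trauma condition explains its exclusion. The third and fourth rows do not meet the same test: an unrelated sign is rightly outside a related-event endpoint. Their fault is the label alone, since a vulval or vaginal sign is genital whatever caused it.

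**Step 4: the CMH sentence.** It speaks of genital AEs, not irritation. It follows directly from the sentence that selects related irritation events, so the natural reading is that both mean the same cluster. Read literally, it is wider, and the paragraph would then use two numerators: irritation events for the confidence limits and genital AEs for the test. Either way the text does not settle which women are counted.

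**The case against.** **The events are compared.** A reader might infer that related bleeding is never compared between arms, or that the trial cannot report its own endpoint. Section 10.10 does not support that. It presents safety summaries across all treatment groups and tabulates related treatment-emergent AEs by system organ class and preferred term for each arm, also by study period. Related metrorrhagia would appear there. What is missing is a formal comparison with it counted as genital. This objection stands and limits the point.

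**Genital AE may have meant the irritation cluster.** Section 10.1 says safety rests on genital irritation and other AEs, which mirrors the endpoint pair, and neither 3.2 nor 10.2.2 says that every genital AE is covered. On that view 10.10 analyzes what was intended. This is a fair reading but not the only one: Section 2.6 reports earlier studies by genital and non-genital AEs and mentions genital irritation separately. Even if the narrow sense was meant, the term is undefined and the label on the remainder is still wrong.

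**Leaving bleeding out of an irritation list is coherent.** Section 16.3.1 allows for an endometrial source. That stands as a reason not to call bleeding irritation. It is no reason to call it non-genital.

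**Burning and discomfort.** One might extend the point to these. The documents do not carry it: Section 6.11 gives burning no body site and pairs discomfort with pain, and genital complaints of either kind could be recorded under listed pain terms or dysuria. Nor does 6.11 show that related metrorrhagia is common, because its list disregards causality and is not said to be ranked.

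**The statistical analysis plan may settle it.** Section 10.8 leaves full details there. But the list, the two-way split and the label are fixed in the protocol itself, so this is a stated rule and not a missing detail.

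**Conclusion.** The point holds as a classification fault. Section 10.10, followed as written, files related metrorrhagia or intermenstrual bleeding as non-genital and, on the contextual reading of the CMH sentence, leaves it out of the formal genital comparison. It also labels as non-genital any irritation sign judged unrelated or due to a pathogen. The endpoint term that should decide these cases is undefined.

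The consequence is limited. The events stay visible by preferred term and arm, so a difference in bleeding between strengths could be seen, though it would not be tested under the genital heading. How many women are affected cannot be derived from the protocol, and any figure would only return assumed rates. The conclusion rests on reading the 10.2.3 list as closed and the CMH sentence as referring to the cluster just before it; the wrong label does not depend on the second reading.

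This should be corrected, because it concerns a named secondary endpoint and the correction is cheap.

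**What to change.** Define genital AE once, by site, and use that definition in the synopsis and in Sections 3.2, 10.2.2 and 10.10. In 10.10, tabulate and compare all genital-tract AEs judged possibly, probably or definitely related, expressly including metrorrhagia and intermenstrual bleeding. Keep the 10.2.3 irritation list as a named subset with its own row; this also keeps apart the events that 10.2.3 solicits actively. Reserve non-genital for events outside the genital tract, and make the CMH sentence name the set it tests.

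If the sponsor did intend only the irritation cluster, the minimum change is to rename the endpoint as related genital irritation in every place and drop the non-genital label from the remainder.

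The cost is a wording change and one more table row. No new data are needed, because AEs are already collected and coded. The reported genital AE rate may be somewhat higher under the wider definition.

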7.1.3 Visit 3 (Day 9-12)

Visit 3 will be scheduled for Day 9-12, after completion of treatment. This visit should be scheduled prior to the anticipated date of onset of menses. If menses is due to occur or actually occurs on Day 9 then the visit may be delayed until complete cessation of bleeding.

This visit will include the following procedures:

- Review of protocol compliance
- · Review diary card
- Review of AEs and concomitant medications (see Sections 7.3.5 and 8)
- Completion of Symptom Questionnaire (see Section 7.2.7)
- Completion of Acceptability Questionnaire [TSQM] (see Section 7.2.8)
- Pelvic examination including vaginal swab for Gram stain, semi-quantitative analysis (subset only) and storage sample (see Sections 7.2.3 and 7.2.6)
- Assessment of BV according to the Amsel's Criteria
- Issue diary card for follow-up period and provide instructions for completion
- Collect used and unused applicators

Women who report no improvement in vaginal discharge associated with BV who wish to receive further treatment will be offered rescue therapy according to Section 6.8. These study participants will be considered "Treatment Non-Responders", and will not attend the TOC visit. Instead, these participants will receive a telephone call at the time that the TOC would be scheduled to assess response to rescue medication and any adverse effects (*e.g.* candidiasis). Participants will be referred to their primary care physician for any ongoing AEs as appropriate. Any ongoing SAEs should be followed until resolution.

Each participant is then provided with the date of the last scheduled visit, the Follow-Up visit.

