9.2 Treatment Non-Responders

A participant will be considered to be a "Treatment Non-Responder" if she reports that the abnormal discharge associated with BV has not improved at Visit 3 and wishes to receive alternative therapy. These participants will not be required to attend the TOC Visit, and will be provided with rescue therapy as per local practice. These women will receive a telephone call at the time that the TOC visit would have been scheduled to assess response to rescue therapy and any adverse effects of the therapy (*e.g.* candidiasis).

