10.4 Sample Size Justification

Primary analysis will be a comparison of 0.5%, 1% and 3% SPL7013 Gel vs. HEC placebo gel with each treatment regimen. Assuming Clinical Cure rates of 50% and 15% for SPL7013 Gel and HEC placebo gel, respectively, a sample size of a minimum of 28 evaluable subjects per treatment arm will provide 80% power to detect a treatment difference with a final alpha significance level of 0.048. It is estimated that there will be a 15% drop-out rate which provides 33 patients to be randomized per treatment arm and 132 patients overall in the study.

The primary hypothesis will be:

Null Hyothesis (Ho): Clinical cure rate at TOC will be the same for both SPL7013

Gel and Placebo treated groups

Alternate Hypothesis (Ha): Clinical cure rate at TOC will be different between SPL7013

Gel and Placebo treated groups

An interim analysis has been included in the sample size design using the using the O'Brien-Fleming method with the significance level calculated for the final analysis being 0.048.

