10.8 Statistical and Analysis Plan

A final statistical analysis plan will be developed and approved by Starpharma prior to database lock. Statistical analyses will be performed after all participants have ended their participation in the study. Participants withdrawn prior to randomization will not be assessed for outcome variables or safety parameters. The following is a summary of the planned analyses; full details are captured in the statistical analysis plan. Any deviations to be made from this summary plan and planned analyses will be documented in the statistical analysis plan.

All hypotheses will be tested for statistical significance with two-tailed p-values unless otherwise noted. Results of all tests will be considered statistically significant if their p-value is less than or equal to 0.048 as per the O'Brien-Fleming α adjustment for the planned interim analysis.

Continuous variables will be summarized using descriptive statistics (N, mean, standard deviation, median, minimum and maximum), while categorical variables will be summarized as counts and percentages of participants in each category. Results will be presented by treatment group as appropriate.

Efficacy analyses will be presented using the MITT and per-protocol populations. For efficacy analyses, all missing values due to participant withdrawal and missed visits as well as values outside of analysis windows will be imputed using the last observation carried forward (LOCF) method as appropriate. For sensitivity analysis, efficacy results will also be presented with "as observed" results.

All baseline and demographic summaries will be based on the MITT dataset. No statistical comparisons between treatment groups will be made on demographic and baseline characteristics.

If there is a discrepancy between the locally and centrally read Nugent score, the locally read score will take precedence over the centrally read score in determining whether a participant is eligible to enter the study. The centrally read score will take precedence over the local score in determining study endpoints.

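### Section 10.10 reports candidiasis and genital irritation signs without separating events before and after rescue therapy, and counts rescue only for relapse

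*Protocol*

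**What the plan says.** All references are to the protocol.

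- **Rescue.** Section 6.8 allows rescue before TOC on two grounds: no improvement in discharge at Visit 3, or return of symptoms between Visit 3 and Visit 4. The therapy is whatever is standard locally. Sections 6.9 and 10.2.6.3 treat it as possibly including antibiotics.
- **Effects of rescue.** Women rescued at Visit 3 receive a "telephone call at the time that the TOC would be scheduled to assess response to rescue medication and any adverse effects" (7.1.3). Section 9.2 describes the same call as made "to assess response to rescue therapy and any adverse effects of the therapy". Both sections give candidiasis as the example.
- **AE window.** Collection runs from first dose to the TOC visit (8.2.1), so it can include time after rescue.
- **Safety analysis.** Women are grouped by treatment actually received (10.2.6.4). Section 10.10 shows AE summaries for the on-treatment period, for follow-up and overall, and adds: "Study period will be based on planned timing of visits". It says explicitly that product use does not define the period.
- **Genital irritation.** One comparison covers events related to study product and not due to a pathogen. A second covers signs irrespective of causality.
- **Candidiasis and rescue.** "The incidence of candidiasis and use of rescue therapy for BV relapse will be presented across all treatment groups". No test is named.

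**The concern.** Rescue is triggered by failure, so it follows efficacy. The plan is sized on "Assuming Clinical Cure rates of 50% and 15% for SPL7013 Gel and HEC placebo gel, respectively"; if that is roughly right, more placebo women than gel women will be rescued, and weaker doses will see more rescue than stronger ones. Candidiasis and genital signs that follow rescue then enter the figures of the gel the woman used earlier. Within follow-up and overall, the tables cannot distinguish a late effect of the gel from an effect of rescue.

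The rescue count printed beside candidiasis should help a reader judge this, but it refers to relapse only. The Synopsis treats relapse as a separate ground from non-improvement at Visit 3. Taken literally, the count leaves out the Treatment Non-Responders.

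Safety and tolerability is a secondary objective (3.2), and the Synopsis names safety as an input to the interim choice of dose groups. With about 33 women per arm, one or two events can change how a table reads.

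**Working it through.** **1. The plan's own figures.** Section 10.10 gives no rescue or candidiasis rates. The cure rates come from section 10.4, so that calculation is reproduced first. It claims "80% power to detect a treatment difference with a final alpha significance level of 0.048"; section 10.8 makes tests two-sided. With rates 0.15 and 0.50, mean 0.325, z = 1.977 and 0.842:

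n = [1.977·√(2·0.325·0.675) + 0.842·√(0.15·0.85 + 0.5·0.5)]² / 0.35² = 27.2, rounded up to 28.

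Then 28/0.85 = 32.9, rounded up to 33, and 4 × 33 = 132. This agrees with the "15% drop-out rate which provides 33 patients to be randomized per treatment arm and 132 patients overall in the study" and is not in dispute.

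**2. Rescue imbalance.** Let s be the share of women not cured who receive rescue before TOC (assumed).
- Placebo: 0.85·s. Active: 0.50·s.
- s = 0.25: 21.2% v 12.5%. s = 0.5: 42.5% v 25%. s = 1 (ceiling): 85% v 50%.

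**3. Spurious difference with no gel effect.** Let b be the background event risk, equal in all arms, and c the added event risk after rescue (both assumed).

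Observed rate = 1 − (1 − b)·(1 − (1 − cure)·s·c)

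Placebo minus active = (1 − b)·0.35·s·c

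| b | s | c | Difference | Women per arm of 33 |
|---|---|---|---|---|
| 5% | 0.25 | 5% | 0.4 points | 0.1 |
| 5% | 0.5 | 10% | 1.7 points | 0.5 |
| 5% | 1 | 10% | 3.3 points | 1.1 |
| 5% | 1 | 20% | 6.7 points | 2.2 |
| 10% | 0.25 | 5% | 0.4 points | 0.1 |
| 10% | 1 | 20% | 6.3 points | 2.1 |

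**4. A true gel excess of 5 points (10% v 5%).**
- s = 0.5, c = 10%: active 1 − 0.90·0.975 = 12.25%; placebo 1 − 0.95·0.9575 = 9.04%; observed +3.2 points.
- s = 1, c = 10%: 14.5% v 13.1%; observed +1.4 points.
- s = 1, c = 20%: 19.0% v 21.15%; observed −2.15 points.

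**5. What the model omits.** It assumes equal detection in every arm. Setting the passages side by side:
- 6.8: women who receive rescue continue to be assessed at the remaining visits.
- 7.1.3 and 9.2: women rescued at Visit 3 do not attend, or need not attend, TOC and are telephoned instead.

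Under the second reading, women rescued at Visit 3 have no TOC pelvic examination and no wet mount, so fewer signs would be found where rescue is commoner. That works against the gel, opposite to steps 3 and 4. The protocol gives nothing from which to size it.

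**6. Why a crude count of pre-rescue events is not enough.** Take s = 0.5, all rescue at Visit 3, and about 40% of the observation time elapsed by then (Day 12 of 30).
- Time at risk retained: placebo 0.575 + 0.425·0.4 = 0.745; active 0.75 + 0.25·0.4 = 0.85.
- An equal 5% risk would show as 5%·0.745 = 3.7% v 5%·0.85 = 4.25%, an apparent harm of the gel created by the cut.

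Person-time rates allow for the different time at risk.

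**The case against.** Much of the plan already limits the problem.

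- Rescue cannot start before Visit 3, after dosing has ended and that visit's assessments are complete. Symptomatic candidiasis is recorded as an AE (7.2.6.4), so it also appears in the AE tables split by period. The on-treatment tables are essentially free of rescue. This stands, but the split is attached to the AE summaries listed before it, not to the candidiasis line or the irritation comparisons, and it cannot separate rescued from non-rescued women within follow-up.
- The product-related comparison needs attribution to study product, made under blinding, and excludes events due to a pathogen. This stands; that comparison is largely protected.
- Section 10.8 leaves full detail to the SAP, and an overall table by treatment is not an error. This stands, but the planned-timing rule and the relapse-only rescue count are fixed in the protocol's wording.

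A reader might go further and infer that SPL7013 Gel will look safer than it is. The documents do not support that. It requires the gel to work, a material event risk after rescue, and equal detection across arms; the telephone call may break the last condition in the other direction. Nor are these tables tied to randomised assignment, since the safety dataset groups by treatment received. Nor is candidiasis formally tested between arms.

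**Conclusion.** The point holds in a limited form. For candidiasis and for genital irritation signs irrespective of causality, the follow-up and overall figures mix gel effects with rescue effects, and the stated rescue count may not show how much rescue each arm received. With b of 5–10%, s of 0.25–1 and c of 5–20%, the distortion is about 0.4 to 6.7 points, or 0.1 to 2.2 women per arm of 33. The upper end needs every woman not cured to be rescued and one in five of those to have an event.

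Only the cure rates come from the protocol; b, s and c are assumptions, and the rescue drug is not fixed. The range favours the gel only because the model assumes equal detection, so the net direction is open. The primary endpoint is unaffected. This is a modest improvement in safety reporting, worth making because it is cheap.

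**What to change.** 1. Keep the overall safety table by treatment received.
2. For candidiasis and for genital irritation irrespective of causality, add a breakdown of events with onset before versus after the first dose of rescue or any other antibiotic. Give the number of women rescued and the person-time at risk per arm, and use person-time rates for the pre-rescue comparison.
3. Replace the relapse-only count with all rescue before TOC, split into non-improvement at Visit 3 and return of symptoms after Visit 3.
4. Reconcile section 6.8 with 7.1.3 and 9.2 on whether rescued women attend the TOC visit, because this decides whether signs are detected equally across arms.

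Items 1 to 3 cost a few lines of text and one extra table; rescue details and AEs are already recorded in the CRF. The downsides are sparse counts and shorter time at risk in rescued women.
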